## 3.0 Objectives

The proposed RCT evaluates a novel form of multi-family group treatment designed to improve community integration (CI) among married/cohabiting OEF/OIF/Persian Gulf Veterans with mTBI, a diagnosis of PTSD, and/or moderate-severe PTS or CS by training spouse/partners to aid with rehabilitation and training both partners to use disability-adapted communication and problem-solving skills to reduce marital conflict and improve marital satisfaction. This intervention, Multifamily Group for Veterans with mTBI for couples (MFG-mTBI-C) builds on an evidence-based treatment for SMI (McFarlane, 2002) by incorporating training on compensatory strategies for cognitive deficits and communication training into the basic problem-solving model. Our specific aims are:

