## **Primary Aims:**

- 1. To evaluate the efficacy of MFG-mTBI-C in improving community integration (*primary outcome*), and interpersonal skills, i.e., anger management, use of social support (*secondary outcomes*) among OEF/OIF/Persian Gulf Veterans with mTBI relative to improvements observed among Veterans participating in a health education group with their partners.
- 2. To evaluate the efficacy of MFG-mTBI-C in reducing caregiver burden (*primary caregiver outcome*) among the spouses/partners of OEF/OIF/Persian Gulf Veterans with mTBI relative to improvements observed for spouses/partners participating in a health education group with the Veteran.

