#### **Secondary and Exploratory Aims:**

 To evaluate the role of gains in Veteran marital satisfaction and emotion regulation and interpersonal skills in mediating improvement in community integration for Veterans participating in MFG-mTBI vs, those participating in a health education group with their partners.

- 4. To evaluate the role of neurocognitive functioning in moderating improvement in community integration for Veterans participating in MFG-mTBI vs, those participating in a health education group for with their partners.
- To evaluate the efficacy of MFG-mTBI-C in reducing PTSD and depressive symptoms relative to reductions observed among Veterans participating in a health education group with their partners.
- 6. To evaluate comparisons between mTBI + PTSD/CS and PTSD/CS 'only' samples,

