Intervention Testing Procedures-Randomization and Maintaining Blind: Following informed consent enrollment, couples will be randomized to one of two treatment conditions (75 to each condition) within each VISN: 1) MFG-mTBI-C, or 2) GHE. To maximize adherence to intervention protocol and avoid inadvertent cross-contamination, each of the two educators at each site will conduct only one intervention, either MFG-mTBI-C or GHE. We will take precautions to ensure the RA's performing outcome assessments and other relevant persons are blind to study condition: 1. Subjects will be randomized to treatment condition using Proc Plan in SAS by an independent research staff member from another project who will place treatment assignments in separate envelopes according to the randomization sequence. To avoid recruitment and/or assessment bias, envelopes will be opened by the independent researcher after informed consent procedures in sequence, and assigned participants will be given a new # according to the randomization schedule; 2. The list linking participant code with treatment assignment will be maintained in a locked cabinet by the PI (who will not perform assessments) and by the study biostatistician (who is in a different location); 3. RA's performing assessments will be blind to educator assignment to treatment condition and will additionally be unaware that each educator is delivering only one treatment. 4. To make # 3 plausible, all educators (and other research staff) will participate in the initial training for both treatments. 5. The PIs will convey new assignments to the appropriate educator who will initiate contact to schedule Joining sessions. 6. All educators will deliver both treatments in closed rooms; 7. The rooms will be equipped identically, with a digital tape recorder; 8. The number and length of sessions will be standardized across conditions; 9. Both MFG-mTBI-C and GHE sessions will be recorded for adherence monitoring so that all participants will have identical files; 10. All data pertaining to session material (e.g., treatment notes) will be stored by educators in a locked or password-protected file separate from that used for assessment data; RA's will not have access to the session files. 11. Participants will be trained not to discuss study procedures except with their study educator or the PI, and study staff (educators and RA's) will only discuss study procedures and assignments with the PI or during supervision. 12. Veterans' VA clinicians will be blind to their treatment assignment; 13. Prior to data analysis, the biostatistician will add an electronic field for treatment group to the data base and the data analyst will be trained not to link assignment with ID code. Thus although RA's will be able to link participant names with ID codes needed for labeling and entering data, etc., they will be blind to treatment assignment using the above measures.

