#### 5.4 Inclusion/Exclusion Criteria

Inclusion criteria-Veterans: Eligible Veterans must have a diagnosis of mTBI in accordance with the VA/DoD Clinical Practice Guideline for Management of Concussion/Mild Traumatic Brain Injury: injury or concussion associated with at least one of the following: brief (< 30 minutes) loss of consciousness or altered state of consciousness or post-traumatic amnesia for < 24 hours following the injury, or they either meet diagnostic criteria for PTSD based on the MINI or have trauma- or CS of at least moderate severity, as defined by either: a) PCL score >34; or b) CES score of >23. Although mTBI-related referrals will be based on a positive DVBIC screen, the diagnosis must be confirmed by Parts A-C of the VA TBI Identification Clinical Interview (Vanderploeg et al., 2012). The TBI must be either blast-related or attributable to another discrete event (e.g., fall, fight, injury) sustained during deployment in the OEF/OIF or Persian Gulf War eras. Post-concussive symptoms (e.g., sleep or memory problems, headache) must not be attributable to a subsequent injury or other pre-existing or concurrent neurologic disorder: Veterans with pre-existing or concurrent neurologic conditions (head trauma, seizures, strokes, neurosurgery, other neurologic impairments based on medical record or self-report) will be excluded. Eligible Veterans must also have a consenting, qualifying spouse/cohabiting partner and a Montreal Cognitive Assessment (MoCA) (Nasreddine,2005) score ≥ 19.The 30item MoCA screens for impairment in specific areas of cognitive functioning deemed necessary for participation in a 90-minute, structured group including attention and concentration, executive functions, language and conceptual thinking. We have specified a MoCA cut-off at the lower end of the range for mild cognitive dysfunction (≥ 19), in order to exclude Veterans with severe memory and/or other cognitive deficits, while admitting those with more mild deficits, as these represent our target population, i.e., Veterans with a history of mTBI, PTSD, and/or moderate-severe PTS or CS.

Inclusion criteria-partners: Legally married to or co-residing with Veteran for at least 6 months, with no plans for divorce or separation.

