### Tests of Specific Study Hypotheses:

### **Primary Hypotheses:**

Hypothesis 1: Veterans with mTBI treated with 6 months of multi-family group for couples (MFG-mTBI-C) will show improved community integration (primary outcome), and improved anger management and use of social support (secondary outcomes) compared with those treated in a health education group without training in communication skills or compensatory strategies; Changes in the primary study outcomes (Sydney Psychosocial Reintegration Scale) from baseline for each treatment group at each time point will be examined using paired t-tests or Wilcoxon signed-rank tests as appropriate. Differences in changes in mean Sydney scores from baseline between two treatment groups will be compared using t-tests or Wilcoxon rank-sum tests as appropriate at each time point. Linear mixed models will be used to examine changes in scales over time and to examine whether the effects of MFG-mTBI-C on the Sydney and secondary Veteran outcomes (DERS and social support scales) vary with time and study sites adjusted for the time-dependent treatment, imbalanced baseline prognostic factors (if applicable), and control variables relating to combat/ injury exposure (mechanism of injury (blast vs. other), # deployments, # TBI's and degree of exposure to war zone violence/threats). In addition, Spearman correlation coefficients will be used to assess associations of changes in the Sydney with changes in Veteran symptoms from baseline at each time point and to examine whether degree of associations increases over time among Veterans treated with MFG-mTBI-C. If significant patterns over time are observed in any of these variables, mixed models will then be used to examine the effects of the variables identified on CI change over 6 months post treatment.

Hypothesis 2: Caregivers whose Veteran spouse/partners are treated with MFG-mTBI-C will show reduced burden (primary caregiver outcome) over the course of treatment and in the 6-month follow-up period relative to caregivers whose Veteran partners are treated in a health education group. The analytic plan proposed in Hypothesis 1 will be used for assessing effects of MFG-mTBI-C on changes in the CBI.

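### The primary aims and Hypothesis 1 claim efficacy in Veterans with mTBI, but the planned analysis estimates a pooled effect that includes Veterans without TBI, and no mTBI-specific estimate is planned

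*Combined protocol and SAP*

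**What the plan says.** **Question asked.** In section 3.0, Primary Aim 1 concerns efficacy "among OEF/OIF/Persian Gulf Veterans with mTBI relative to improvements observed among Veterans participating in a health education group". Primary Aim 2 concerns caregiver burden "among the spouses/partners of OEF/OIF/Persian Gulf Veterans with mTBI". In section 5.6, Hypothesis 1 states that "Veterans with mTBI treated with 6 months of multi-family group for couples (MFG-mTBI-C) will show improved community integration", and the exploratory hypotheses on PTSD and depressive symptoms name the same population. The abstract's closing sentence is about benefit to Veterans with mTBI.

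**Population enrolled.** Section 5.4 admits Veterans with mTBI "or they either meet diagnostic criteria for PTSD based on the MINI or have trauma- or CS of at least moderate severity", the last defined by PCL >34 or CES >23. The abstract and section 5.1 give the same alternatives. The opening of section 3.0 describes the population as "Veterans with mTBI, a diagnosis of PTSD, and/or moderate-severe PTS or CS". No minimum mTBI share is set.

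**Allocation and analysis.** Under section 5.1, "couples will be randomized to one of two treatment conditions (75 to each condition) within each VISN"; TBI status is not a factor. The General Approach in section 5.6 keeps every randomised participant in the principal analyses. The Hypothesis 1 mixed model adjusts for number of TBIs and mechanism of injury (blast or other). It contains no interaction of treatment with mTBI status.

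**The one aim that separates the groups.** Exploratory Aim 6 reads "To evaluate comparisons between mTBI + PTSD/CS and PTSD/CS 'only' samples". Section 5.6 gives it no hypothesis, method or power.

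**The concern.** The population in the primary question is narrower than the population analysed. If the plan is followed as written, a pooled effect will be reported under an mTBI label whatever the mTBI share turns out to be. A null result could reflect dilution. A positive result would not show how much of the effect arose in mTBI couples.

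The documents give reasons to expect some difference in effect. Table 6 names Veterans with TBI and their partners as the target group of MFG-mTBI-C, and compensation for TBI-related deficits as its content. The educational workshop in Table 7 is about TBI. The Education component described in section 5.1 works partly by re-attributing behaviour to the mTBI.

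Two further gaps follow from the same mismatch. Mechanism of injury has no defined value for a Veteran without TBI, so the written model cannot be run unambiguously on everyone randomised. Aim 6 leaves out Veterans with mTBI but no PTSD/CS, and its wording does not say that treatment effects are what is to be compared.

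**Working it through.** **1. What the pooled analysis estimates.** Let f be the mTBI share (equal in both arms), D the effect with mTBI and D0 the effect without:

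pooled effect = f·D + (1 − f)·D0

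This equals D only if D0 = D or f = 1. The plan neither tests the first condition nor secures the second.

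**2. The plan's own power figure.** Table 8 (Sydney, effect .5, two-sided alpha 0.05) gives .87, .85 and .83 for 76, 72 and 67 per cell. The normal approximation is power = Φ(d·√(n/2) − 1.96). With d = 0.5:

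- n = 76: Φ(3.082 − 1.96) = 0.869
- n = 72: Φ(3.000 − 1.96) = 0.851
- n = 67: Φ(2.894 − 1.96) = 0.825

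These agree with the table. The plan defines effect size as (mt−mc)/mc. With the pilot Sydney change of 3.9, an effect of .5 is a difference of 3.9 × 0.5/1.5 = 1.3. The change SD is not stated; the value that fits all nine Table 8 cells is about 2.59, and 1.3/2.59 ≈ 0.50. So d = 0.5 is a fair translation for the Sydney.

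**3. Evaluable numbers.** Section 5.1 plans 75 per arm. At 20% attrition, one of the plan's own scenarios, 75 × 0.80 = 60 per arm. (The power tables start from 90 per cell, which is a separate inconsistency.) Undiluted power is Φ(0.5·√30 − 1.96) = 0.78.

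**4. Range over f.** Assumptions: D = 0.5, D0 = 0, the same SD with and without TBI.

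- Pooled: Φ(0.5f·√30 − 1.96)
- mTBI only: Φ(0.5·√(60f/2) − 1.96)
- Interaction: Φ(0.5/√[2/(60f) + 2/(60(1−f))] − 1.96)

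| f | mTBI per arm | Pooled effect | Pooled power | mTBI-only power | Interaction power |
|---|---|---|---|---|---|
| 90% | 54 | 0.45 | 0.69 | 0.74 | 0.13 |
| 75% | 45 | 0.375 | 0.54 | 0.66 | 0.22 |
| 50% | 30 | 0.25 | 0.28 | 0.49 | 0.28 |

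**5. A milder assumption.** If D0 is half of D, the pooled effect is 0.5 × (f + 0.5(1 − f)), that is 0.475, 0.4375 and 0.375. Pooled power is then about 0.74, 0.67 and 0.54.

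**6. CBI.** With the pilot change of 18.0, an effect of .5 is 18.0 × 0.5/1.5 = 6.0. The SD that fits Table 9 is about 12.6, so d ≈ 0.476. With 60 per arm, undiluted power is 0.74. An mTBI-only comparison has about 0.70, 0.62 and 0.45 at the three shares.

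**7. Size needed for an mTBI-only test.** For 80% power at d = 0.5, n = 2 × (1.96 + 0.842)²/0.25 ≈ 63 evaluable per arm. Then 63/0.80 gives 79 per arm, or 158 Veterans with mTBI. That implies about 211 randomised in total at f = 75% (158/0.75) and 316 at f = 50% (158/0.50).

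**The case against.** The wider population is stated openly. The opening of section 3.0, the target population in section 5.4 and the DSMB rationale in section 6.0 all name it. Hypothesis 2 does not itself mention mTBI, and the abstract's first hypothesis is not restricted to it. Much of the mismatch is therefore unrevised wording. That stands, and it makes the repair easy, but rewording alone leaves the mTBI question without an estimate.

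No effect at all without TBI is an extreme case. The Introduction says that the problems often cannot be attributed specifically to TBI, and that the treatment shares elements with couples treatments for PTSD. This also stands: the figures in step 4 are a bound rather than a forecast, and at a 90% share the loss is modest. Nothing in the documents supports an effect confined to couples without TBI.

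A reader might infer three stronger things, which the documents do not support:

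- *That the trial cannot answer the mTBI question.* TBI status is a baseline characteristic, so a comparison restricted to mTBI keeps the protection of randomisation even without stratification. It is unplanned and probably underpowered, but not invalid.
- *That the primary model ignores TBI.* It adjusts for number of TBIs and mechanism of injury. What it lacks is a term that lets the treatment effect differ by mTBI status.
- *That chance imbalance in mTBI status between arms would confound Aims 4 and 6.* A treatment-by-mTBI analysis conditions on that status, so imbalance costs precision only. For Aim 4, section 5.6 already controls for imbalanced baseline prognostic factors, although mTBI status is not among its named examples.

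**Conclusion.** The point holds for the planned analysis. Aims 1 and 2, Hypothesis 1 and the exploratory hypotheses are about mTBI, whereas the analysis returns an average over an unstated mix of Veterans with and without TBI. Reporting that average as mTBI efficacy would require equal effects in the two groups, which the plan does not examine.

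The size cannot be fixed from the documents because the mTBI share is not given. If the effect is confined to mTBI, pooled power falls from 0.78 to between 0.69 and 0.28 as the share goes from 90% to 50%; if the effect without TBI is half as large, it falls to between 0.74 and 0.54. These figures rest on 20% attrition from 75 per arm, d = 0.5 with mTBI, equal SDs and independent couples. An mTBI-specific estimate will be imprecise at the planned size, and the interaction test has power of at most about 0.28. Both are worth having for honest estimation with confidence intervals, and neither can serve as a decisive test.

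**What to change.** 1. Reword Primary Aims 1 and 2, Hypothesis 1, the exploratory hypotheses and the abstract's concluding sentence to the enrolled population (mTBI and/or PTSD, PTS or CS), and label the pooled result accordingly.
2. Add baseline mTBI status and its interaction with treatment to the Sydney and CBI models. State how the pooled effect is obtained once the interaction is present, for example as the average over the enrolled mix. Report the mTBI-stratum effect with its confidence interval as the basis for any mTBI-specific statement, and acknowledge its low power.
3. Define Aim 6 as this analysis and state where Veterans with mTBI but no PTSD/CS are counted. Define the injury covariates for Veterans without TBI: for example, number of TBIs set to zero, and blast versus other coded only among those with mTBI, alongside the mTBI indicator.
4. Apply the existing TBI screen and confirmatory interview to all Veterans. Section 5.4 ties the interview to mTBI-related referrals and does not say that Veterans entering by the PTSD/CS route receive it, so a uniform mTBI variable is not yet assured.

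Stratifying randomisation by mTBI status within VISN is optional. It would improve precision, but it adds strata to an allocation that must already fill small groups in both arms in tandem.

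The cost is revised text, one added covariate and interaction in each model, and interview time for any Veterans who would not otherwise have been classified. No increase in sample size is needed for the reworded primary question on this account.

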#### **Secondary and Exploratory Aims:**

 To evaluate the role of gains in Veteran marital satisfaction and emotion regulation and interpersonal skills in mediating improvement in community integration for Veterans participating in MFG-mTBI vs, those participating in a health education group with their partners.

- 4. To evaluate the role of neurocognitive functioning in moderating improvement in community integration for Veterans participating in MFG-mTBI vs, those participating in a health education group for with their partners.
- To evaluate the efficacy of MFG-mTBI-C in reducing PTSD and depressive symptoms relative to reductions observed among Veterans participating in a health education group with their partners.
- 6. To evaluate comparisons between mTBI + PTSD/CS and PTSD/CS 'only' samples,

## 5.0 Study Procedures

## 5.1 Study Design

Overview: 150 Veterans with a positive DVBIC screen for deployment-related mTBI sustained during the OEF/OIF/Persian Gulf eras confirmed by Parts A-C of the VA TBI Identification Clinical Interview (Vanderploeg et al, 2012), with reported loss of consciousness < 30 minutes or if they either meet diagnostic criteria for PTSD based on the Mini International Neuropsychiatric Interview (MINI) or have trauma- or combat-related stress (CS) of at least moderate severity, as defined by either a PTSD Checklist (PCL) score >34 (Kimerling, 2009) or Combat Exposure Scale (CES) score >23 (Keane et al., 1989), a consenting spouse/cohabiting partner and a Montreal Cognitive Assessment (MoCA) (Nasreddine, 2005) score ≥ 19 will be randomized to receive either: 1) six months (12 bi-monthly sessions) of MFG- mTBI-C, a psychoeducational rehabilitation and skills-building intervention after 2-3 individual couples "Joining" sessions; or 2) six months (12 bimonthly sessions) of Group Health Education (GHE), a structured didactic intervention delivering information and general recommendations to address health problems common in the OEF/OIF/Persian Gulft cohort. Participants will be assessed pre-treatment, immediately post-treatment, and 6 months post-treatment. A Diversity Committee will ensure representative ethnic/racial enrollment and cultural competence. The Diversity Committee will be chaired by [name] and will additionally comprise a member from each site with expertise in ethnicity/racial issues, including treatment, recruitment and retention in clinical research ([name], JJP VAMC and [name], VAMHCS). Prior to enrollment, the committee will help each site develop a diversity recruitment plan, individualized to the local catchment area, participating facilities and support groups. Weekly coordinator calls throughout the study will include a discussion of ethnic minority enrollment rates for each site. A committee member will attend a call monthly to review enrollment, retention and develop enhanced outreach strategies if goals are not being met. Data will be analyzed using an intent-to treat analysis with paired comparisons between treatment groups on primary (Veteran community integration) and secondary (Veteran interpersonal skills, marital adjustment, caregiver burden) outcome variables using mixed effects regression models. The study research tasks and our timeline to achieve them are presented in Table 4 below.

Table 4: Timeline of Research Tasks

Months	Research Task
0-5	Refine manual, develop adherence scale for control condition, Train educators
	and research assistants, IRB submission, approval
4-5	Specify procedures for random assignment; blinding assessors, develop
	databases, refine recruitment procedures with study and facility staff

5-38	Enroll and study 150 cases (75 treatment, 75 control); Follow-up assessments
39-44	Complete follow-up on last cohorts' cases for 6 months
44-48	Analyze, disseminate data

Tempo: In order to study 14 groups of 3-5 couples each (7 treatment, 7 control) per VISN (3 and 5), each VISN will begin recruitment and individual sessions for two groups, one treatment, one control in study month 5, and continue to enroll and initiate treatment for two additional groups, one in each study condition, every 4-5 months until all groups have been completed and followed, in study month 44. This design will in most cases avoid a long wait for participants between randomization and starting treatment. In cases where one treatment condition becomes "filled", in order to avoid long delays and possible attrition before starting treatment, and permit both interventions to be conducted in tandem, we will allow groups with as many as 8 and as few as 3 couples. The protocol also permits an additional "Joining" session to keep early enrolled couples engaged while later-enrolled couples are being assessed and 'joined". In terms of workload, although there will be overlap between groups, the more labor-intensive work of recruiting, consenting and meeting with individual couples will overlap with the less intensive bi-monthly group meetings for the previously-enrolled two groups and will therefore be feasible.

**Assessment:** Participants will be assessed pre- and post-treatment and 6 months post-treatment (*Table 5 below*). Partners will be assessed within 2 weeks of the corresponding Veteran assessment. Assessors will be trained to reliably administer all clinical instruments, using the PI, a psychologist or psychiatrist experienced with these measures, as a 'gold standard.' [name], neuropsychologist based at the VAMHCS's, will establish reliability on the VA TBI Identification Clinical Interview through independent ratings of 10 interviews and will then supervise the RA at their site on administration and scoring of this interview and other neurocognitive measures on a weekly basis. An *Assessment Committee* comprised of Drs. [name], and [name] will meet bi-weekly to plan and implement training, monitor reliability via periodic checks, and implement corrective procedures as needed.

